#### Follow-ups

Survey data collected in Phase 1 will be treated as baseline or 0-month data. Table 1 shows the schedule for subsequent study assessments. The CFQ, SF-12 and EQ5D-5D will be completed by the patient online or via a paper form returned to the research office. The 3m follow-up allows us to see any changes between those receiving the intervention and those not. The 6-month (6m) follow-up enables us to see if any benefits observed at 3m are maintained beyond the intervention period, and to compare this between the two groups.

	0m (baseline)	3m	6m
CFQ	Х	Х	Х
SF-12	Х	Х	Х
EQ-5D-5L	Х	Х	Х
Intervention diary		X (intervention group only)	X
Qualitative interview		X	X

Table 1: Assessments and timescales for the feasibility study

Proposed Primary outcome measures: These will be the logistical findings arising from the feasibility study (i.e. related to the conduct of the trial)

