#### Purpose

## The purpose of the feasibility study is to address the following questions:

1. Can we use an online screening questionnaire to determine the prevalence of physical and mental fatigue associated with 'Long COVID-19'?

2. Can we recruit and retain participants into a Randomised Controlled Trial (RCT) which tests a lymphatic self-massage intervention, spinal mobility exercises and alternating warm and cool gel packs on the upper spine over 3 months to alleviate fatigue related symptoms for those affected by the longer-term sequelae of COVID-19?

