#### Phase 2: Wait-list RCT Intervention Study

Those eligible will receive a PIS and CF explaining the Phase 2 RCT study either by email or by post. After 5 days, participants will be telephoned by a research practitioner based in Northern Care Alliance NHS Foundation Trust's Research delivery team.

100 participants providing informed consent will be allocated 1:1 into a two-arm wait-list randomised control trial (RCT) comparing lymphatic self-massage technique (the intervention) plus any usual care (UC) from their healthcare professionals vs. UC alone. This means any treatment received by participants will not be constrained. Those in the intervention group will receive instructions and equipment required via post as soon as they are randomised, with the UC wait-list group receiving their equipment 3 months later (after completion of their 3m follow-up), meaning all Phase 2 participants will be given access to the intervention. Both groups will be asked to complete follow-up measures at 3m and 6m.

Qualitative interviews will be conducted with 10 participants in the intervention arm at 3 months and a further 10 in each of the intervention arm and UC arms at 6 months to assess acceptability of the intervention, adherence to the intervention (over time for intervention group) and to explore potential barriers and drivers to its use.

#### **Detailed Plan of Investigation** 7

Research Activity		Done	Year and Month										Responsible		
			1 2 3 4 5 6 7 8 9 10 11 12 13 14 15								15				
		-	*	4	2 4	-	0	1	0 3	10	11 12	13		13	
re-work: On run up to	research becoming active											L			
PPIE	Consultation and patient input	1	L									L			LR/RP
FARSITE	Agree FARSITE search criteria with NW e-Health/CRN	-	L									L			LR/AH/CRN
	Run FARSITE search - Indicative numbers		L									L			CRN
Qualtrics Survey	Set up Phase 1 survey	-	L									L			SB/LR/AH/RP/MH
	Set up & test Phase 2 eligibility checks	-	L									L			SB/LR/AH
	Set up Phase 2 surveys at 3m and 6m		L									L			SB/LR/AH
Approvals	Sponsorship		L									L			AH/LR
	Ethical application (IRAS)		L									L			AH/LR
hase 1: Online Survey	Capacity & Capability checks: Salford & GM		H	-	-	-	-	-	_		_	-	-	-	AH/LR
Engagement with GP			4	-	_	-		-	-			-	-		SB LR / RA (CRN)
Survey launch	Eligible patients receive invite from their GP		5						-			-	-		SB
Survey launch	Implied consent by completing survey - 0m data		- 2					-		+		-	-		GP Staff (CRN)

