#### Randomisation for Phase 2 Intervention RCT

Randomisation will be carried out using an internal STATA routine (Chaimani et al. 2013) by an independent member of the University of Manchester Biostatistics Group who will be responsible for this, along with conveying the allocation to the RA in order for the intervention pack to be sent to participants. This method ensures the statistician carrying out the analyses (MH) remains masked to treatment allocation.

Eligible participants will be allocated at random (1:1) in blocks of size 4, 6 or 8 (chosen at random and in equal numbers) to either the immediate lymphatic self-massage intervention plus UC or UC alone plus the intervention from 3 months. Due to the known gender differences between women and men both in terms of CFS/ME and also Long COVID itself, we will stratify for gender within the randomisation. We will set up the randomisation so that should extra sites outside of Salford be required to achieve recruitment targets, we will ensure a balance between the two trial arms.

All Phase 2 participants will receive a letter thanking them for completing the Phase 1 survey and letting them know which group they have been allocated to. The letter will explain how RCTs work and the importance of follow-up data irrespective of which group participants are allocated to, and that all participants will receive the intervention described but at different times, and that they will be followed up for 6 months in total (at 3m and 6m) using the same survey measures they have already completed in the baseline survey. One additional tick sheet will be used to capture participants' use of the intervention which will be sent to the intervention participants at 3m and 6m and to the control – wait-list group at 6 m only.

The group randomised to receive the intervention will receive this immediately after randomisation along with this letter. The UC wait-list control group will be sent the intervention pack after submission of their 3m follow-up data. We will not tell patients when to stop using the intervention but will monitor its use in the two study arms over time.

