#### 7.5 Outcome measurement

- 1. To determine the participation rate for an online survey of Long COVID within general practice.
- 2. To determine the prevalence of Long COVID using a case cut-off of 4 or above on the CFQ (binomially scored)
- 3. To determine recruitment and retention of participants into an RCT which tests a lymphatic self-massage intervention over 6 months to alleviate fatigue related symptoms for those affected by the longer-term sequelae of COVID-19.

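### The 6-month between-arm comparison describes immediate versus delayed start; it cannot compare maintenance of benefit between the groups, as the protocol says it will

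*Protocol*

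**What the plan says.** Section 7.1, Follow-ups, gives the two assessments different purposes. The 3-month one looks for differences between those who have had the intervention and those who have not. The 6-month one "enables us to see if any benefits observed at 3m are maintained beyond the intervention period, and to compare this between the two groups".

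Other parts of the protocol bear on whether this is possible:

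- **End of use.** Section 7.1, Randomisation: "We will not tell patients when to stop using the intervention but will monitor its use in the two study arms over time". Under Qualitative Interviews, the protocol foresees that some participants will carry on past 3 months.
- **Controls.** Section 7.1, Randomisation: "The UC wait-list control group will be sent the intervention pack after submission of their 3m follow-up data". Section 6 describes the same arrangement, "meaning all Phase 2 participants will be given access to the intervention", and Intervention components repeats it.
- **End of follow-up.** Assessments are at 3 and 6 months, and section 7.3 caps participation at 6 months.
- **Length of the intervention.** The study question in section 1 has "alternating warm and cool gel packs on the upper spine over 3 months", and the timetable in section 7 shows a 3-month intervention phase for each arm. Section 7.5 speaks of an RCT that "tests a lymphatic self-massage intervention over 6 months".
- **Aims.** Section 5 lists two separate comparisons: use versus non-use at 3 months, and the effect of delaying use, with no time point.
- **Analysis.** Section 10 plots changes from baseline to 3 and 6 months by arm with 95% confidence intervals. It also derives likely effect sizes for a range of measures to size a larger trial, without fixing the time point.

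**The concern.** To compare maintenance between two groups, each group must be assessed after its own intervention phase has ended. To attribute what is seen to the intervention, some group must remain untreated over the same months. From 3 to 6 months this design provides neither: controls start the intervention in that window and are last seen at the end of it.

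The 6-month between-arm difference is then open to misreading in either direction. A small difference could mean that the immediate arm lost its benefit, or that controls caught up. Stable scores in the immediate arm could reflect lasting benefit, continued use or natural recovery.

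The definitive trial is also affected. Section 10 does not say which assessment supplies the effect sizes. In the secondary outcomes only the CFQ comparison is placed at 3 months. The SF-12 comparison has no time point. The QALY comparison is put over 9 months, which is longer than follow-up, and any span past 3 months includes time when controls have been offered the intervention. A 6-month contrast could therefore be carried forward as if it were an effect against usual care.

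**Working it through.** The protocol states no figure for the 6-month comparison, so there is none to reproduce. The check is a timeline followed by simple algebra.

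**1. Timeline (months from randomisation, forms on schedule, nominal 3-month phase)**

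| | Immediate arm | Wait-list arm |
|---|---|---|
| Intervention starts | 0 | 3 at the earliest |
| Nominal phase ends | 0 + 3 = 3 | 3 + 3 = 6 at the earliest |
| Last assessment | 6 | 6 |
| Observed after own phase | 6 − 3 = 3 | 6 − 6 = 0 at most |

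The wait-list entry for maintenance is empty. If the 3-month form comes back late, the pack goes out late too. The nominal phase then ends after month 6. The protocol gives no figure for lateness, so this is not quantified.

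**2. The between-arm difference at 6 months**

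Let d be the 3-month effect of immediate use against usual care, with improvement counted as positive. Let m be the share of d still present in the immediate arm at 6 months, and c the effect in controls at 6 months as a share of d. Randomisation gives both arms the same expected natural course, so it cancels:

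- 3-month difference = d
- 6-month difference = (m − c) × d

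| m | c | 6-month difference |
|---|---|---|
| 1 | 1 | 0 |
| 0.5 | 0.5 | 0 |
| 0 | 0 | 0 |
| 1 | 0.5 | 0.5 d |
| 0.5 | 0 | 0.5 d |

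The difference alone does not identify m. Assuming c = 1 would recover m, but the protocol does not state that assumption.

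**3. Adding the within-arm changes**

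Section 10 also plans changes by arm, which carry more information. Let g be the natural change from 3 to 6 months:

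- immediate arm, 3-to-6-month change = g + (m − 1) × d
- wait-list arm, 3-to-6-month change = g + c × d

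With g = 0, the case (m, c) = (1, 1) gives 0 and d, while (0, 0) gives −d and 0. These are plainly different. They coincide only if g differs between the two cases by the whole of d: with g = d, the case (0, 0) gives d − d = 0 and d + 0 = d. The half-and-half case with g = 0.5 d gives 0.5 d − 0.5 d = 0 and 0.5 d + 0.5 d = d, again the same pair.

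So with d taken from the 3-month comparison, two observed changes have to fix three unknowns (g, m, c). An assumption about g closes the gap. The controls' change from 0 to 3 months informs that assumption but does not replace a concurrent untreated arm.

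**4. What m would mean**

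Even if recovered, m describes scores under whatever use participants chose after month 3. It is not persistence after use has ended.

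**The case against.** The strongest reply is that the 6-month data are not reduced to one number. Section 10 plans changes by arm, and tick sheets record use at 3 and 6 months in the intervention arm and at 6 months in the wait-list arm. A pattern in which the immediate arm holds and controls improve looks quite unlike one in which the immediate arm slips back and controls stay flat. This stands. A reader might infer from the algebra that the 6-month data can never tell such patterns apart. The documents do not support that: the ambiguity is complete only for the between-arm difference taken alone. What remains is that reading the within-arm changes needs an assumption about natural course, and that those who stop are a self-selected group.

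A reader might also infer that there is no intervention period at all, or that the protocol sets two conflicting ones. Neither is supported. Section 1 and the timetable give a nominal 3-month phase. The 6 months in section 7.5 sits in an item on recruitment and retention and may mean trial follow-up. The wording needs reconciling, but the main point does not depend on it.

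It is also fair to say that section 5 already names the effect of delay as an aim, that Follow-ups places the treated-versus-untreated contrast at 3 months, and that the time point for effect sizes is often left to a SAP. The first two make the correction easy. On the third, a SAP could fix the time point, but no analysis can supply a control-arm assessment that the design does not take.

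**Conclusion.** The Follow-ups sentence is wrong as written in one respect: maintenance beyond the intervention period cannot be compared between the two groups. Controls have no assessment after their own 3-month phase, and no untreated arm exists from 3 to 6 months. The 6-month between-arm difference cannot identify how much of the 3-month benefit is kept, since very different combinations give the same value. The immediate arm's 3-to-6-month change remains a legitimate description under self-chosen use, and the 6-month contrast remains valid for immediate versus delayed start.

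The timeline assumes forms on schedule and a nominal 3-month phase. The algebra assumes only that randomisation equalises expected natural course, and d is not given a value.

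The weight is moderate. No formal testing is planned, and the primary feasibility outcomes are recruitment and retention, which this does not touch. A reader might infer that the trial will report a null 6-month difference as lost benefit. Nothing in the protocol says so; that is a risk of the present wording, not a stated plan. What changes is what may be concluded at 6 months and which effect sizes go forward.

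**What to change.** Three wording changes:

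1. **Section 7.1, Follow-ups.** State that the 6-month between-arm comparison describes immediate versus delayed start, matching the last aim in section 5. State that the 3-to-6-month change in the immediate arm is a within-arm description reported alongside recorded use, and is not evidence of persistence after stopping or of effect versus usual care.
2. **Section 10.** State that intervention-versus-usual-care effect sizes used to plan the definitive trial come from the 3-month assessment only.
3. **Intervention period.** Reconcile the wording in section 1, the section 7 timetable, section 7.1 (Randomisation and Follow-ups) and section 7.5, so that a reader can tell the nominal intervention phase from the length of follow-up. No rule on when use should stop is proposed here.

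The cost is a few sentences. No visit, measure or change in sample size is needed. The sponsor gives up one claim that the design could not support.

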#### Secondary 'Clinical' Outcome measures;

**Chalder Fatigue Questionnaire (CFQ) (Chalder et al., 1993)**: Our data analysis of CFQ scores at 3m will compare those who have used the intervention (on an intention to treat ITT basis – i.e. assuming those randomised to receive the intervention use it as intended) vs those who have not.

**SF-12** (https://www.rand.org/health-care/surveys\_tools/mos/12-item-short-form.html): This self-reported outcome measure developed from the Medical Outcomes Study assesses the impact of health on an individual's everyday life. It is often used as a quality-of-life measure and will be used to see if differences exist in quality of life between the two groups.

**Euroquol EQ-5D-5L (htpps://euroquol.org)**: This will permit us to calculate change in quality of life and determine Quality Adjusted Life Years scores (QALYs) for the intervention and waitlist control comparison group over 9m.

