#### 7.6 Withdrawal criteria

Participants will be allowed to withdraw from the study at any point. We will not collect any further data from this participant however will use data available during their time in the study for the final study analysis. If it is in the participant's best interest the clinician in charge of the study (AH) may also choose to withdraw the participant in the interests of their own health.

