# 10 Statistical analyses and data handling

#### Analysis

This is a feasibility study, so we will not be carrying out formal hypothesis testing to determine if the intervention is effective. Data analysis will follow an Intention-To-Treat (ITT) protocol and will be used to inform power calculations for a definitive trial in addition to other published sources. Attrition and reasons for drop-out will be recorded where possible. We will assess rates of missing data (and which elements in particular) and proportions of dropouts at different trial stages. We will also assess whether any of the measures display floor and/ or ceiling effects.

We will calculate and present in a CONSORT (Eldridge et al, 2010) flow chart: the proportion of people with CFQ scores greater than or equal to 4, consenting to the study; those entering the randomised phase; the proportion completing 50% and 100% intervention (using patient reported compliance sheet); the proportion completing follow-up assessments at 3 and 6 months post-randomisation.

We will summarise, as appropriate (e.g. mean/ standard deviation; median/ inter-quartile range; proportion/ 95% confidence interval; data range) data for all potential outcome measures, overall and by group. Outcome data and changes (mean differences) in patient-reported measures between baseline (initial clinical assessment) and 3 and 6 month follow-up will be plotted with 95% confidence intervals by randomisation group on an intention to treat basis.

Adherence with the intervention will be measured and used to calculate an estimate of dose response. Where participants adhere to all 3 stages of the intervention fully – using the intervention as intended daily this will be deemed full intervention, with non-use of any stages of the intervention as a zero dose.

The SD of the (potential) Primary Outcome, along with the estimated attrition rate and the average number recruited per PCT/CCG (plus the range of this data) will be used to help inform the sample size calculation for the large-scale RCT.

The Primary feasibility outcomes will be recruitment and retention rates, and we will gain an estimate of likely effect sizes of the self-help intervention for a range of outcome measures and based on this determine the appropriate sample size for a larger trial to evaluate its effectiveness and cost-effectiveness versus standard treatments delivered within an NHS CFS/ME Service.

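### The 3-month CFQ comparison is worded by use and misdescribes intention to treat, and section 7.6 ends data collection at every withdrawal, including one made by the study clinician

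*Protocol*

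**What the plan says.** **The comparison.** In the protocol, section 7.1, under Secondary 'Clinical' Outcome measures, the CFQ analysis at 3 months "will compare those who have used the intervention (on an intention to treat ITT basis". The bracket explains that basis as "assuming those randomised to receive the intervention use it as intended) vs those who have not".

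Section 10 (Analysis) states the general principle: "Data analysis will follow an Intention-To-Treat (ITT) protocol". It adds that outcomes and changes "will be plotted with 95% confidence intervals by randomisation group on an intention to treat basis". Actual use has its own place there: "Adherence with the intervention will be measured and used to calculate an estimate of dose response". Section 5 frames the 3-month aim as intervention group against wait-list control group.

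**Withdrawal.** Section 7.6 lets participants leave the study at any time and then says: "We will not collect any further data from this participant". Data already held are kept for the final analysis. The study clinician "may also choose to withdraw the participant in the interests of their own health". No separate data rule is given for that case.

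**Schedule and purpose.** Table 1 in section 7.1 has one baseline and two later assessments, at 3 and 6 months, completed online or on paper. Section 6 allocates 100 participants 1:1. Section 10 names recruitment and retention as the primary feasibility outcomes, plans no formal hypothesis test, and uses the SD, attrition and likely effect sizes to plan a larger trial.

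**The concern.** Intention to treat keeps everyone in the arm to which they were allocated, whatever they did. It needs no assumption that the intervention was used, and its estimate already includes the effect of non-use. The CFQ sentence instead names the groups by use and turns the principle into an assumption of full adherence. The protocol itself expects non-use: section 10 defines a zero dose, and section 7.1 plans interviews with people who never start. The likely harm is one of interpretation: an as-randomised difference could be presented as the effect of using the intervention as intended.

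The withdrawal rule raises a separate issue, missing outcomes. A withdrawal made for health reasons may well be related to fatigue or quality of life. Before 3 months only one arm has the intervention, so such withdrawals may also fall unequally. A participant whose part is ended by the clinician may be quite willing to complete a questionnaire at home, yet the text rules this out. That person then counts as lost in the retention figure and in the attrition rate carried to the next trial.

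**Working it through.** **1. Which groups are compared?** No arithmetic applies, so the statements are set side by side.

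| Place | Groups named |
|---|---|
| Section 5, aims | Intervention group and wait-list control group |
| Section 7.1, CFQ | Those who used the intervention and those who did not, with everyone allocated to it counted as a user |
| Section 10, Analysis | Randomisation group |

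If everyone allocated to the intervention counts as a user, the users are the intervention arm. The wait-list arm receives its pack only after submitting 3-month data (sections 6 and 7.1), so the non-users are the wait-list arm. The CFQ contrast is then the as-randomised one and agrees with sections 5 and 10. The groups are right and the explanation is wrong.

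**2. Who loses an outcome under section 7.6?** The post-baseline assessments are at 3 and 6 months only.
- Withdrawn before 3 months: neither outcome is obtained.
- Withdrawn between 3 and 6 months: the 6-month outcome is lost.

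The rule that earlier data are kept helps only the second group.

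**3. Effect on retention.** Arm size is 100 / 2 = 50. One withdrawal is 1/50 = 2 percentage points of that arm's retention. An assumed 5 withdrawals are 5/50 = 10 percentage points.

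**4. Effect on precision.** The protocol gives no withdrawal rate, so the rates here are assumptions, taken as equal in both arms. In SD units, the 95% half-width for a difference in means is 1.96 × √(2/n).

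| Withdrawn before 3 months | n per arm | Half-width (SD) |
|---|---|---|
| 0% | 50 | 0.39 |
| 10% | 45 | 0.41 |
| 20% | 40 | 0.44 |
| 30% | 35 | 0.47 |

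**5. Effect on the estimate.** Suppose a fraction w of the intervention arm is withdrawn, their outcomes would have been d SD worse than those of the rest of the arm, and the wait-list arm is complete. The full-arm mean is worse than the observed mean by w × d. With d = 0.5 SD (assumed):
- w = 10%: 0.10 × 0.5 = 0.05 SD
- w = 20%: 0.20 × 0.5 = 0.10 SD
- w = 30%: 0.30 × 0.5 = 0.15 SD

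Each is well below the half-widths in step 4, but it runs in one direction, in favour of the intervention.

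**The case against.** A reader might infer from the CFQ sentence that the stated analysis is as-treated and so not intention to treat at all. The stakes would then be large. Take no true effect, a fraction a of the arm using the intervention, non-users 0.5 SD worse in prognosis, and non-users pooled with the 50 controls. The bias is 0.5(1 − a)/a + 0.5(1 − a)/(2 − a), which is 0.21 SD at 80% use, 0.48 SD at 60% and 0.94 SD at 40%. A next trial sized on a full-use effect would be too small by 1/a²: 1.56-fold at 80% use and 4-fold at 50%.

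The protocol does not support that reading. The bracket counts everyone allocated to the intervention as a user, sections 5 and 10 compare by group, and section 10 keeps actual use for a separate dose-response estimate. An as-randomised estimate already contains non-use, so a trial sized on it is not under-sized on that account. None of these figures measures the point made here.

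On withdrawal, the other side has a fair case. Collecting nothing after someone leaves a study is ordinary, and it creates missing outcomes without changing the analysis groups. Stopping use is not called withdrawal: section 7.1 says only that use will be monitored. Section 10 already reports completion of the intervention separately from completion of follow-up, with reasons for drop-out where possible. Clinician withdrawal is discretionary, nothing suggests it will be common, and the handling of missing data may be set out in an analysis plan that is not at hand.

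All of that stands. It leaves two things untouched: the explanation of intention to treat is wrong as written, and section 7.6 itself forbids further collection from people who may not have declined it. An analysis plan cannot recover data that the protocol says will not be collected.

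**Conclusion.** Both points hold in limited form, at moderate to minor severity. The CFQ sentence misdescribes intention to treat and should be aligned with section 10; the analysis groups do not change. The withdrawal rule creates avoidable missing outcomes that may be related to outcome and may differ by arm, and they count against a primary feasibility outcome.

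The size depends on how many such withdrawals occur, which the protocol does not say. Each costs 2 percentage points of an arm's retention. At an assumed 10 to 30% in one arm, with those withdrawn 0.5 SD worse, the shift in the CFQ difference is 0.05 to 0.15 SD. That health-based withdrawals are the participants with worse outcomes is plausible but is an inference. CFQ is a secondary outcome in a feasibility study without formal testing, so no conclusion about efficacy turns on this. The estimates do feed the planning of the larger trial, which is why the correction is worth making.

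**What to change.** **Section 7.1, CFQ paragraph.** Replace the description by use with: *CFQ at 3 months will be compared between arms as randomised, regardless of whether or how much the intervention was used.* Remove the assumption about use. The dose-response estimate in section 10 stays as a separate analysis.

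**Section 7.6.** State that the 3- and 6-month questionnaires continue to be sent to anyone who stops the intervention or is withdrawn from it, unless the participant declines further follow-up. Report intervention discontinuation and loss to follow-up separately by arm. This concerns data collection only. Who is withdrawn, and on what clinical grounds, is left as it stands.

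**Cost.** A few lines of protocol text, one line in the participant information sheet, and a few more questionnaires. Under section 8.2 the change needs the sponsor's agreement before it goes to the ethics committee. The sample size stays at 100.
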